4.3. Other

Condition	Type	Identifier	Source/Instructions	Additional information expected?	Important PD
Any performed assessment not required by study protocol	M	PD_MM.141	Monitor PD / i.e., extra labs, PFTs or MRIs; For CDDM only: to be coded once		No
Other violations of Informed consent procedures	M	PD_MM.002	Monitor PD / e.g., wrong or draft version, wrong language, missing information (signature time...)		No
E-diary not used at any visit	M	PD_MM.199	Monitor PD / For CDDM only: to be coded once		No
Data provided by site to external vendors containing potential patient identifiers	M	PD_MM.153	Monitor PD / Vendor data / e.g., real date of birth, subject's initials		No
Any applicable assessment or report not signed (except central laboratory) and/or not dated	M	PD_MM.174	Monitor PD / e.g., ECG, PFT or MRI reports; Includes reports not signed and/or not dated; For CDDM only: to be coded once		No
Any central laboratory report signed and dated more than 5 calendar days after receipt	M	PD_MM.138	Monitor PD / Includes reports not signed and/or not dated; For CDDM only: to be coded once		No
Any performed assessment not following the study protocol requirements	M	PD_MM.142	Monitor PD / Valid only if not covered by another PD code For CDDM only: to be coded once per deviation type		No
Any other study protocol deviation	M	PD_MM.183	eCRF / Monitor PD / For CDDM only: to be coded once per deviation type		No
Plasma concentration of teriflunomide measured earlier than 20 weeks after last study intake	M	PD_MM.200	Monitor PD		Yes

	TPL-100062 Protocol Deviation Code List
Protocol Number: AC-058B301 Acronym: OPTIMUM	

Any site personnel made aware of Central laboratory report containing flags (e.g. L or H flags) for blinded lymphocytes or white blood cell counts (except Visit 1 and Visit 2).	M	PD_MM.212	Vendor data / Monitor PD / For CDDM only: to be coded once per occurrence. To be reported in FDM database ONLY based on ACM listings as the information is potentially unblinding.	\Original report date\\\	No
--	---	---------------------------	---	--------------------------	----

16 APPENDICES

A. Adverse Events of special interest

Adverse events of special interest (AESIs) include the anticipated risks of treatment with ponesimod and events that may be related to MS comorbidities.

The definitions for AESIs are based on the systematic approach using Standardized MedDRA Queries (SMQ). The additional relevant terms can be added to the search or deleted appropriately providing the rationale for the change. The proposal is based on MedDRA version 21.0. The following safety areas are addressed by the pre-defined AESIs:

- **Effect on heart rate and rhythm AESI (including hypotension)**

Effect on heart rate and rhythm AESI are identified by the preferred terms (PT) in the following SMQ: Bradyarrhythmias (including conduction defects and disorders of sinus node function) (SMQ) [20000053]. In addition, the following PT will be added to the search for AEs addressing effects on heart rate and rhythm: ‘Bradycardia’, ‘Electrocardiogram RR interval prolonged’, ‘Heart rate decrease’, ‘Presyncope’, ‘Syncope’, ‘Loss of consciousness’, ‘Chronotropic incompetence’, and ‘Central bradycardia’.

Hypotension will be identified searching the following PT: ‘Blood pressure decreased’, ‘Blood pressure diastolic decreased’, ‘Blood pressure orthostatic decreased’, ‘Blood pressure systolic decreased’, ‘Diastolic hypotension’, ‘Hypotension’, ‘Mean arterial pressure decreased’, ‘Orthostatic hypotension’, ‘Procedural hypotension’, ‘Circulatory collapse’, ‘Blood pressure fluctuation’, ‘Labile blood pressure’ and ‘Blood pressure ambulatory decreased’.

- **Hypertension AESI**

Hypertension AESI are identified by the PT in the following SMQ: Hypertension SMQ (narrow scope) [20000147].

- **Hepatobiliary disorders / Liver enzyme abnormality AESI**

Hepatobiliary disorders/ Liver enzyme abnormality AESI are identified by the PT in the following SMQ: Drug related hepatic disorders – comprehensive (SMQ) (broad scope) [20000006]. This SMQ is included in the SMQ Hepatic disorder (SMQ) but only the PT included in Drug related hepatic disorders - comprehensive search (SMQ) are included to identify hepatobiliary disorders / Liver enzyme abnormality AESI.

- **Pulmonary AESI**

These AEs are identified by the PT the in the following SMQs: Asthma/bronchospasm (SMQ) (broad scope) [20000025] or Interstitial lung disease (SMQ) (broad scope)

[20000042]. The PT 'Dyspnoea at rest', 'Dyspnoea', 'Dyspnoea exertional', 'Carbon monoxide diffusing capacity decreased', 'Pulmonary function test abnormal', 'Pulmonary function test decreased', 'Vital capacity abnormal', and 'Vital capacity decreased' are added to the search pre-defined by SMQs Asthma/bronchospasm or Interstitial lung disease.

- **Macular edema AESI**

Macular edema AESI are identified by the following PT: 'Macular oedema', 'Macular hole', 'Macular pseudohole', 'Macular rupture', 'Macular cyst', 'Retinal oedema', 'Diabetic retinal oedema', 'Cystoid macular oedema', 'Papilloedema', and 'Pseudopapilloedema'.

- **Infection AESI**

Infection AESI are identified by the adverse events belonging to the SOC (System Organ Class) Infections and Infestations (SOC), only if reported as serious or severe.

- **Herpetic infection AESI**

Herpetic infection AESI are identified by the PT in the following high level terms: Herpes viral infections (HLT) and the following preferred terms will be added to the search for AEs addressing varicella zoster infection: 'Encephalitis post varicella', 'Herpes gestationis', 'Herpes simplex test positive', 'Human herpes virus 6 serology positive', 'Human herpes virus 8 test positive', and 'Herpes virus test abnormal'.

- **Skin malignancy AESI**

Skin malignancy AESI are identified by the PT in the following SMQs: Skin neoplasms malignant and unspecified (SMQ) (broad scope) [20000173].

- **Non-skin malignancy AESI**

Non-skin malignancy AESI are identified by the PT in the following SMQ: Malignant or unspecified tumours (SMQ) (broad scope) [20000091] excluding the PT which included in the following SMQs: Skin neoplasms, malignant and unspecified (SMQ) (broad scope) [20000173].

- **Seizure AESI**

Seizure AESI are identified by any preferred term in the following SMQ: Convulsions (narrow scope) (SMQ) [20000079].

B. Protocol Deviation code list

Protocol deviations are defined as per the Protocol Deviation code list, version 4, 8 June 2018. Protocol deviations are categorized according to the categories in the Protocol

C.2. FSIQ-RMS Symptoms score

Daily Symptoms Scores:

FSIQ-RMS Symptoms Daily scores (**FSIQ-RMS SDS_{c_Dj}**) will be calculated for each day D_j of assessment as 0 to 100 score using following equation:

$$\text{FSIQ-RMS SDS}_{c_Dj} = \frac{(\text{Sum of non-missing items 1, 2, 3, 4, 5, 6, 7) at } D_j}{\text{Number of non-missing items} * \text{Highest rating (10)}} * 100,$$

Daily scores will be derived at each day (where day refers to study day from randomization) with assessment. If for a given day, more than 3 out of the 7 items are missing in the Diary, then the Symptoms daily score **FSIQ-RMS SDS_{c_Dj}** will be set to missing.

Weekly Symptoms Scores:

FSIQ-RMS Symptoms Weekly Scores (**FSIQ-RMS SWS_{c_wi}**) within a 7 consecutive day period (Week i) are calculated from daily scores **FSIQ-RMS SDS_{c_Dj}** as follows:

$$\text{FSIQ-RMS SWS}_{c_wi} = \frac{\text{Sum of the non-missing FSIQ-RMS SDS}_{c_Dj}}{\text{Number of non-missing diary days at Week}_i},$$

if the number of missing daily scores is < 4 (i.e. at least 4 daily scores are available).

If more than 3 daily scores are missing (i.e., less than 4 daily scores are available), the weekly score **FSIQ-RMS SWS_{c_wi}** cannot be calculated and is considered missing.

Weekly scores are derived for the following time points W_i: Baseline (Pre-randomization period), Visits 6 (Week 12), 7 (Week 24), 10 (Week 60), 12 (Week 84) and 14 (Week 108).

Visits will be assigned based on time windowing [see Section 11.3]. The weekly score for a visit is derived based on the 7-day time period with non-missing weekly score. Preference is given to 7-day time periods with (i) minimum number of missing daily scores and (ii) with the seventh day being closest to target. If two periods are equally close to target the worst score is considered.

Baseline Symptoms Weekly Score will be derived during the closest 7-day time period prior to and including randomization date in which a non-missing weekly score can be derived.

Change from baseline **FSIQ-RMS SWS_c** to each assessment visit (**CHN FSIQ-RMS SWS_{c_Base_wi}**) will be derived as: Weekly score (**FSIQ-RMS SWS_{c_wi}**) – Baseline score (**FSIQ-RMS SWS_{c_Base}**).

C.3. FSIQ-RMS impacts domain

FSIQ-RMS impact sub-domain scores are derived as a weekly 0 to 100 score. They are derived based on the second part of the questionnaire based on questions referring to the last 7 days. Weekly scores are therefore derived based on questions answered during a single day.

Each sub-domain score is defined based on 5 items. If at least 3 of these 5 items are available, the scores can be derived. Otherwise it is considered missing. Formulae for derivation are provided below.

FSIQ-RMS Physical Impacts Weekly score:

$$\text{FSIQ-RMS-PIWS}_{c\ w_i} = \frac{(\text{Sum of non missing items 1, 5, 6, 8, 13}) \text{ at Week}_i}{\text{Number non missing items} * \text{Highest rating (4)}} * 100$$

FSIQ-RMS_c Cognitive/Emotional Impacts Weekly score:

$$\text{FSIQ-RMS-CEIWS}_{c\ w_i} = \frac{(\text{Sum of non missing items 2, 3, 7, 9, 10}) \text{ at Week}_i}{\text{Number of non missing items} * \text{Highest rating (4)}} * 100$$

FSIQ-RMS Coping Impacts Weekly score:

$$\text{FSIQ-RMS-CIWS}_{c\ w_i} = \frac{(\text{Sum of non missing items 4, 8, 11, 12, 13}) \text{ at Week}_i}{\text{Number of non missing items} * \text{Highest rating (4)}} * 100$$

Scores are derived for the following time points W_i : Baseline (Pre-randomization period), Visits 6 (Week 12), 7 (Week 24), 10 (Week 60), 12 (Week 84) and 14 (Week 108). Visits will be assigned based on time windowing [see Section 11.3].

Baseline is defined as last available score prior to and including randomization date. Change from baseline is defined as absolute change from baseline.

C.4. SF-36 scoring

Recoding items

Scores for each question response are indicated on the questionnaire. Firstly, seven of the questions are reverse scored, to ensure that a higher item value indicates better health (Items 11b & 11d, 9a & 9e, 6, 9d & 9h). Three of the questions also need to be recalibrated. These are question 1 and questions 7 and 8. Recalibration and reverse score items are as follows:

Precoded and final values for Item 7

Response choices	Precoded Value	Final Value
None	1	6.0
Very mild	2	5.4
Mild	3	4.2
Moderate	4	3.1
Severe	5	2.2
Very Severe	6	1.0

Precoded and final values for item 8 where both items 7 and 8 are answered

Response choices	Item 8 Precoded	Item 7 Precoded Value	Item 8 Final value
Not at all	1	1	6
Not at all	1	2 through 6	5
A little bit	2	1 through 6	4
Moderately	3	1 through 6	3
Quite a bit	4	1 through 6	2
Extremely	5	1 through 6	1

Precoded and final values for item 8 where item 7 is not answered

Response choices	Item 8 Precoded	Item 8 Final Value
Not at all	1	6.0
A little bit	2	4.75
Moderately	3	3.5
Quite a bit	4	2.25
Extremely	5	1.0

Precoded and Final Values for Item 1

Response choices	Precoded Value	Final Value
Excellent	1	5.0
Very Good	2	4.4
Good	3	3.4
Fair	4	2.0
Poor	5	1.0

Precoded and Final Values for Items 11a & 11c, and 11b & 11d

Response choices	Precoded Item Value	Final Value Items 11a & 11c	Final Value Items 11b & 11d
Definitely true	1	1	5
Mostly true	2	2	4
Don't know	3	3	3
Mostly false	4	4	2
Definitely false	5	5	1

Precoded and Final Values for Items 9a - 9i

Response choices	Precoded Item Value	Final Value Items 9a, 9d, 9e, 9h	Final Value Items 9b, 9c, 9f, 9g, 9i
All of the time	1	5	1
Most of the time	2	4	2
Some of the time	3	3	3
A little of the time	4	2	4
None of the time	5	1	5

Precoded and Final Values for Item 6

Response choices	Precoded Value	Final Value
Not at all	1	5
Slightly	2	4
Moderately	3	3
Quite a bit	4	2
Extremely	5	1

Computing domain scores

The raw score for each domain is then calculated as the sum of the scores for the items in that domain, as shown in [Table 12](#). For example the raw score for role physical is the sum of the scores for items 4a, 4b, 4c and 4d. The next step is to transform each raw domain score to a domain scale 0–100 score. This is calculated as follows:

$$(\text{Actual raw score} - \text{lowest possible raw score}) / \text{Possible raw score range} \times 100$$

where the possible raw score range is the highest possible raw score for that domain minus the lowest possible raw score for that domain. This transformation converts the lowest and highest possible scores to 0 and 100, respectively. Scores between these values represent the percentage of the total possible score achieved. All except one of the 36 items (Item 2 self-reported health transition) are used to score the eight SF-36 domains. Each item is used in scoring only one domain. The table below provides the information necessary to apply the above formula to each domain.

Table 12 Scoring and transforming scales

Domain	- Raw Domain scores (individual final item value range)	Lowest possible raw score	Highest possible raw score	Possible raw score range
Physical Functioning	3.a to j (1-3)	10	30	20
Role-Physical	4.a to d (1-5)	4	20	16
Bodily Pain	7# + 8# (1-6)	2	12	10
General Health	1# + 11.a + b* + c + d* (1-5)	5	25	20
Vitality	9.a* + e* + g + i (1-5)	4	20	16
Social Functioning	6* + 10 (1-5)	2	10	8
Role-Emotional	5.a + b + c (1-5)	3	15	12
Mental Health	9.b + c + d* + f + h*(1-5)	5	25	20

[†] Sum of the final item values after recalibrating and recoding.
 * indicates items with reversed scores

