5.4.2 Secondary efficacy variables

5.4.2.1 Change from baseline to Week 108 in fatigue-related symptoms as measured by the FSIQ-RMS symptoms score

The Fatigue Symptom and Impact Questionnaire-Relapsing Multiple Sclerosis (FSIQ-RMS) is a validated patient reported outcome instrument from which a fatigue symptoms score and sub-domain impact scores can be obtained, where higher scores indicate greater fatigue or impact [Protocol appendix 9]. The questionnaire consists of 2 parts: section 1 is a daily diary and is answered during 7 consecutive days. Section 2 is a weekly diary and is answered on the 7th day of the 7 consecutive days where the daily diaries were filled in. The questionnaire is completed using an electronic device that automatically tracks the completion date. Data are transferred electronically to the sponsor.

FSIQ-RMS is completed during the pre-randomization period (i.e., at Visit 2: 7 consecutive days preceding the randomization [Baseline visit]), and during the post-randomization period, i.e., at scheduled Visits 6, 7, 10, and 12 (Weeks 12, 24, 60, 84, respectively), 14 (Week 108), as well at premature EOT visit and at unscheduled visits (due to relapses or other unscheduled visits). If applicable, it is also completed at the corresponding visits in the PTO. For more details refer to [Table 2–Table 4](#).

FSIQ-RMS **symptoms domain (FSIQ-RMS-S)** consists of 7-items assessing fatigue related symptoms collected as a daily diary (section 1) on an 11-point numeric rating scale (0–10) with a 24-hour recall period.

The **FSIQ-RMS-S score** may be computed as a daily or weekly 0 to 100 score (higher score implies greater fatigue). To be able to compute a daily symptoms score, at least 4 items of the symptoms diary must be non-missing; otherwise the score is considered “missing”. For each 7-day weekly score, at least 4 reported diaries with at least 4 items completed on each diary day are needed to calculate the FSIQ-RMS-S weekly score. If fewer than 4 diaries with data on at least 4 items are available within the 7-day period, then the weekly score is considered as “missing”. Details of the scoring rules to calculate FSIQ-RMS-S daily and weekly scores as well as rules to define baseline and post baseline FSIQ-RMS-S weekly scores are given in the Appendix [C.2](#).

Change from baseline in FSIQ-RMS symptoms score is defined as the absolute change from baseline to each time point.

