11.3 Re-assignment of premature EOT visits / Visit windowing

For all parameters unless stated below: For subjects who discontinued study drug prematurely with available premature EOT visit, the visit may be re-assigned to a scheduled visit as follows:

- If a result is missing for a scheduled visit, it can be replaced with a result from a premature EOT visit available in the respective visit window [see [Table 9](#)].

Table 9 Premature end of treatment remapping

Visit window	Nominal value Day	Lower limit for Day	Upper limit for Day
Week 2	15	2	22
Week 4	29	23	70
Week 12	85	71	126
Week 24	169	127	210
Week 36	253	211	294
Week 48	337	295	378
Week 60	421	379	462
Week 72	505	463	546
Week 84	589	547	630
Week 96	673	631	714
Week 108	757	715	Open end

Day refers to treatment day, i.e., days from study treatment start.

MRI: For MRI measurements visit windowing of premature EOT visits is conducted using ± 3 months around the target day (Week 60: Day 330 to Day 512; Week 108: \geq Day 665) to account for the less frequent assessment schedule.

Patient reported outcomes collected on electronic device: For patient reported outcome data collected via an electronic device visit windowing is applied as a general process. Rationale is that incorrect visit labels are not corrected via a query process whereas the questionnaire date is tracked automatically by the device therefore, the latter is considered to provide most reliable information. Questionnaires based on dates will be assigned to the visits based on [Table 10](#). If multiple questionnaires are available, the one closest to target is selected.

Physician reported questionnaire and other composite assessment data [REDACTED] [REDACTED] Nominal visits are considered. If missing at the nominal visit, data from a premature end of treatment visit (if not available or appropriate then from an unscheduled visit) is assigned to the visits based on [Table 10](#). If multiple unscheduled assessments qualify the one closest to target is selected.

Table 10 Visit windowing for questionnaire and psychometric assessment data

Visit window	Nominal value Day	Lower limit for Day (Week)	Upper limit for Day (Week)
Baseline	-1	Open end	1
Week 12	85	2 (W0+)	126 (W18)
Week 24	169	127 (W18 ⁺)	294 (W42)
Week 60	421	295 (W42 ⁺)	504 (W72)
Week 84	589	505 (W72 ⁺)	672 (W96)
Week 108	757	673 (W96 ⁺)	Open end

Day refers to study day, i.e., days from randomization date. Wx+ = after week x.

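### The FSIQ-RMS weekly-score rule ranks completeness above closeness to target, so a fuller relapse or unscheduled diary from up to 84 days earlier can replace a valid scheduled Week 108 score

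*SAP*

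**What the plan says.** SAP Section 5.4.2.1 schedules the FSIQ-RMS symptoms diary at Weeks 12, 24, 60, 84 and 108, "as well at premature EOT visit and at unscheduled visits (due to relapses or other unscheduled visits" included. It refers the reader to Appendix C.2 for how baseline and post-baseline weekly scores are defined.

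Section 11.3 assigns diaries to visits by date: "For patient reported outcome data collected via an electronic device visit windowing is applied as a general process". Its stated reason is that wrong visit labels on the device are not queried, whereas the completion date is tracked automatically. The Table 10 row begins "Week 108 757 673" (target day, then lower limit) and has no upper limit. Where a window holds more than one record, Section 11.3 says: "If multiple questionnaires are available, the one closest to target is selected".

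Appendix C.2 gives a different order for post-baseline weekly scores: "Preference is given to 7-day time periods with (i) minimum number of missing daily scores and (ii) with the seventh day" nearest the target day. A further rule settles ties: "If two periods are equally close to target the worst score is considered". A weekly score is valid "if the number of missing daily scores is < 4 (i.e. at least 4 daily scores are available". For baseline, C.2 takes the nearest 7-day period up to randomization that yields a valid score, with no preference for completeness.

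Section 9.1.1 puts fatigue first in the fallback sequence. Section 9.7.1.2 tests the Week 108 difference in least-square means at 0.05/3.

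**The concern.** The endpoint is fatigue at Week 108. Under C.2 as written, a subject whose scheduled diary has one day missing can be represented at Week 108 by a complete diary triggered by a relapse weeks earlier. Nothing in the SAP excludes such a diary or gives precedence to the scheduled one.

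Other parts of the SAP guard against this kind of substitution:

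- Section 11.3 takes physician-reported data from the nominal visit, and uses premature end-of-treatment or unscheduled data only if that is missing.
- Section 5.4.2.2.1 leaves out an unscheduled MRI that is not the last scan.
- Section 5.4.2.3.1 does not allow an EDSS taken during a relapse to confirm disability accumulation.

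Relapse diaries arise in proportion to relapses, which are the primary outcome, so the number of substitutions may differ between arms. The fatigue result also decides whether CUAL is tested with one third or two thirds of alpha. The supportive analyses in Section 9.7.1.3 (delta adjustment, LOCF, on-treatment data, per protocol) do not vary the selection rule.

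**Working it through.** **The plan's own figures.** Week 108 target: 108 × 7 + 1 = Day 757. Lower limit: 96 × 7 + 1 = Day 673. Both match Table 10. The local level is 0.05/3 = 0.0167.

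**Reach of the rule.** 757 − 673 = 84 days, or 12.0 weeks, if only the seventh diary day must fall in the window. If all seven days must fall in it, the earliest seventh day is Day 679, and 757 − 679 = 78 days (11.1 weeks).

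**The two orderings applied to test cases.** C.2 is taken as fewest missing days, then distance of the seventh day from Day 757, then worst score. Section 11.3 is taken as distance only.

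| Scheduled diary | Relapse diary | C.2 selects | 11.3 selects |
|---|---|---|---|
| Day 757, 6/7 | Day 673, 7/7 | relapse | scheduled |
| Day 757, 4/7 | Day 720, 5/7 | relapse | scheduled |
| Day 757, 7/7 | Day 673, 7/7 | scheduled | scheduled |

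Replacement therefore needs strictly fewer missing days in the other diary. At equal completeness the diary nearer target is kept.

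**Size (illustration only).** The SAP gives none of these inputs. Assumed: comparator relapse rate 0.2-0.4 per year; rate ratio 0.7; one diary per relapse; independent daily completion of 80-95%, equal for both kinds of diary; relapse diaries 5-20 points worse.

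1. Chance of a relapse in the 84 days = 1 − exp(−rate × 84/365.25).
   - Comparator: 1 − exp(−0.2 × 0.230) = 4.5%, up to 1 − exp(−0.4 × 0.230) = 8.8%.
   - Ponesimod, at rates 0.14 and 0.28: 3.2% to 6.2%.
2. Chance that a relapse diary outranks a valid scheduled one = Σ over k = 1 to 3 of P(scheduled misses k) × P(relapse misses fewer than k), divided by P(scheduled misses at most 3). Missing days are binomial with n = 7. Results: 0.345 at 80% completion, 0.307 at 90%, 0.222 at 95%.
3. Share of subjects replaced.
   - Comparator: 0.045 × 0.222 = 1.0%, up to 0.088 × 0.345 = 3.0%.
   - Ponesimod: 0.032 × 0.222 = 0.7%, up to 0.062 × 0.345 = 2.2% (unrounded inputs).
4. Shift in the Week 108 difference = (difference in relapse probability) × (replacement chance) × (excess score).
   - Smallest: (0.0450 − 0.0317) × 0.222 × 5 = 0.015.
   - Largest: (0.0879 − 0.0624) × 0.345 × 20 = 0.176.

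**Yardstick.** Section 9.7.1.3.1 sets the delta increment at 0.5 and describes it as one tenth of the meaningful change, so the implied threshold is 0.5 × 10 = 5 points.

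**The case against.** **Completeness first has a proper use.** C.2 forms weekly scores from any seven consecutive days, so one diary yields several overlapping periods. Take a full diary on Days 747-753. The period ending Day 753 has 7/7 scores at distance 4. The period ending Day 756 has 4/7 at distance 1. Ranking by closeness alone would pick the second and discard three observed days. This stands, and it rules out simply reversing the two criteria. It does not justify carrying the preference across separate diaries weeks apart, and C.2 does not confine it to one diary.

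**Visit labels are unreliable.** Section 11.3 says so, and a remedy that relies on the label of the scheduled diary would ignore it. This also stands; the scheduled episode has to be found by date.

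**C.2 is the governing rule.** Section 5.4.2.1 sends the reader there, and a specific rule normally overrides a general one. A reader might infer that C.2 and Section 11.3 leave the score undetermined. The documents do not support that: C.2 can be taken to govern. Section 11.3 nevertheless states its rule without exception, so the precedence should be written down.

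**The direction is not certain.** A reader might infer an established bias toward ponesimod. That would need fewer relapses on ponesimod, worse fatigue in relapse diaries, and relapse diaries complete enough to win; the SAP establishes none of these. Premature end-of-treatment and other unscheduled diaries are also eligible, with unknown direction.

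**Conclusion.** The point holds as a fault in the derivation rule. Followed literally, C.2 can put an off-target diary into the Week 108 fatigue test in place of a valid scheduled one, and relapse frequency affects how often. This reading takes (i) and (ii) as ranked. The numbering and the tie-break on closeness support it, although C.2 does not say so in words.

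The size is small: about 0.01-0.18 points against an implied 5, under assumed relapse rates, completion rates and excess fatigue. The shift favours the arm with fewer relapses only if fatigue is worse in relapse. Nothing here shows that the test result would change, nor that most relapse diaries in the window would displace a scheduled score. The case for correcting it is that the endpoint is alpha-controlled, the substitution may be related to treatment, and the correction is cheap.

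**What to change.** Revise the post-baseline rule in Appendix C.2 as follows:

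- Group daily scores into diary episodes by date, and define in the text how episodes are separated and how an episode's distance from target is measured.
- Among episodes with at least 4 daily scores in a 7-day period, choose the one closest to target.
- Use completeness only to choose the 7-day period within that episode, or to break ties between episodes.
- State that a diary linked by date to a relapse or unscheduled visit does not replace a valid episode at the scheduled visit, with that visit identified by date and not by device label.
- State in Section 11.3 that C.2 governs the FSIQ-RMS symptoms score.

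In the examples above, this keeps the Day 747-753 diary whole and selects the scheduled Day 757 diary over the Day 673 relapse diary. The cost is SAP wording and a modest programming change, with no new data. The downside is that some scores will rest on 4-6 days instead of 7.

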2.1.1 Periods

The study consists of the following protocol defined periods:

- **Pre-randomization period** starts with signature of the Informed Consent Form (ICF) and ends with subject's randomization and lasts up to 45 days (per screening attempt). Subjects can be re-screened once.
- **Treatment period** starts on the day of randomization immediately after the 1st dose of study drug intake (Visit 3–Day 1 of the study) and continues until the premature discontinuation of study drug or the scheduled End-of-Treatment (EOT) visit at Week 108. Subjects receive double-blind treatment throughout the treatment period. The treatment period consists of a titration and a maintenance phase.
 - A 2-week titration scheme is implemented on Day 1 (or at re-initiation following a treatment interruption of more than 3 days) to reduce the first-dose effect of ponesimod [see [Table 1](#)].
 - The titration phase is followed by the maintenance phase with one capsule of ponesimod 20 mg or teriflunomide 14 mg administered orally once daily in the morning (from Day 15 to End-of-Treatment [EOT]).

- **Post-treatment period** starts immediately after the last dose of study drug and ends with the End-of-Study visit. It comprises the post-treatment safety follow-up (FU) period and if applicable, the PTOp. During the post-treatment period, all subjects undergo the accelerated elimination procedure of teriflunomide lasting for 11 days with administration of cholestyramine (8 mg three times daily, or if not tolerated 4 mg three times daily) or activated charcoal (50 g two times daily), see protocol for details.
 - **Post-treatment safety follow-up period**
For subjects who enter the extension study AC-058B303, the safety FU period ends with the FU1 visit (scheduled 14–22 days after last dose of study drug). If they have not complied with the teriflunomide accelerated elimination procedure at the time of FU1, it ends with the abbreviated FU2 visit (scheduled 23–37 days after the last dose of study drug).

For subjects who do not enter the extension study, the safety FU period ends with FU2 visit (scheduled 30–37 days after last dose of study drug).
 - **Post-treatment observation period**

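### The baseline fatigue score lacks the fewest-missing-days preference used after baseline, so complete baseline diaries can lose one to three of their seven days, at a small cost in precision

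*SAP*

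**What the plan says.** SAP Section 5.4.2.1 describes the symptoms part of the questionnaire: "section 1 is a daily diary and is answered during 7 consecutive days". It schedules the baseline diary "at Visit 2: 7 consecutive days preceding the randomization [Baseline visit", and says that the "rules to define baseline and post baseline FSIQ-RMS-S weekly scores are given in the Appendix" (C.2).

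Appendix C.2 calculates a weekly score "if the number of missing daily scores is < 4 (i.e. at least 4 daily scores are available"). It then gives two statements on which seven days to use:

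- For visits assigned by time window: "Preference is given to 7-day time periods with (i) minimum number of missing daily scores", and after that to the period whose seventh day is nearest the target day.
- For baseline: the "closest 7-day time period prior to and including randomization date in which a non-missing weekly score can be derived". This sentence contains no completeness criterion.

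The baseline score is subtracted in every change score. Under Section 9.7.1.2 it also enters the MMRM as a covariate and in a baseline-by-visit interaction. Fatigue comes first in the fallback sequence of Section 9.1.1, at 0.05/3.

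**The concern.** The baseline rule starts from the randomization date and moves back only until a window holds four daily scores. It does not start from the diary, and it stops at the first window that qualifies even when a fuller one lies a day or two earlier. Valid diary days already in the database are then left out of the baseline mean. After baseline, the appendix prefers the fullest week.

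At stake is measurement error in the baseline score. A noisier covariate explains less of the Week 108 variance, so the treatment contrast is estimated slightly less precisely. The endpoint is tested at one third of alpha, and its success passes alpha on to the lesion endpoint, so precision given away without a stated reason is worth recovering if that is cheap.

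**Working it through.** The SAP gives no standard deviation, day-to-day variance or power for this endpoint, so there is no figure of its own to reproduce. The check has two parts: what the rule does to a complete diary, and what that could cost.

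**1. Days used from a complete diary.** Let the seven consecutive diary days end g days before randomization, with g = 0 meaning that the last entry is on the randomization date. There is no study day 0 (Section 11.1), so the window ending on randomization covers Days -6 to -1 and Day 1. Apply each rule to all 7-day windows ending on or before randomization, requiring at least 4 scores.

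| g | Baseline rule as written | Fewest missing first, then closest |
|---|---|---|
| 0 | 7 | 7 |
| 1 (diary on Days -7 to -1) | 6 | 7 |
| 2 | 5 | 7 |
| 3 | 4 | 7 |
| more than 3 | 4 | 7 |

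For g above 3 the window slides back only until it catches four entries. On the schedule in Section 5.4.2.1 the loss is one day, or none if the last entry falls on the randomization date. Larger gaps are possible: the pre-randomization period "ends with subject's randomization and lasts up to 45 days (per screening attempt"), and the baseline row of Table 10 ("Baseline -1 Open end 1") has an open lower limit. The SAP does not say how common such gaps are.

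**2. Error variance of the baseline mean.** With independent daily errors the ratio to a full week is 7/m for m days: 7/6 = 1.17, 7/5 = 1.40, 7/4 = 1.75.

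**3. Effect on the adjusted contrast.** Assumed, not from the SAP: between-subject SD sb = 20, daily SD se = 10 to 20, true baseline-to-Week 108 correlation rho = 0.7, seven days at Week 108, independent daily errors. Residual variance after adjustment:

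V(m) = sb² + se²/7 − (rho·sb²)² / (sb² + se²/m), with (0.7 × 400)² = 78,400.

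- se = 10: V(7) = 414.29 − 78,400/414.29 = 225.04. V(6) = 414.29 − 78,400/416.67 = 226.13, a rise of 0.5%. V(4) = 414.29 − 78,400/425 = 229.81, a rise of 2.1%.
- se = 20: V(7) = 457.14 − 78,400/457.14 = 285.64. V(6) = 457.14 − 78,400/466.67 = 289.14, a rise of 1.2%. V(4) = 457.14 − 78,400/500 = 300.34, a rise of 5.1%.

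Confidence intervals widen by the square root: about 0.2-0.6% if every baseline used 6 days, and 1.0-2.5% if every baseline used 4. In equivalent subjects, 1133 × (1 − V(7)/V(m)) gives about 5-14 for 6 days and 23-55 for 4.

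**4. Sensitivity.** For rho from 0.5 to 0.8 and the same daily SDs, the rise is 0.2-2.0% with 6 days and 0.8-8.2% with 4. A second parameterization (proportion of daily-score variance due to the person 0.5-0.9, rho 0.6-0.8) gives about 0.1-2% and 0.6-8%. In its 4-day case, 80% power at 0.05/3 would become about 76-80%. With day-to-day errors autocorrelated at 0.5, the 4-day rise is about 0.9-6%.

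**The case against.** The best counter-argument is that the completeness preference already covers baseline. Appendix C.2 lists Baseline among the time points, assigns visits by the windows of Section 11.3, and Table 10 gives Baseline its own window with target Day -1. The baseline sentence could then merely confine the period to on or before randomization. On that reading a Day -7 to -1 diary keeps all seven days. But the sentence sets its own criterion, the closest period with a derivable score, and that criterion would have no effect if the general order decided the choice. If both readings were thought tenable, two programmers could derive different baselines, and the wording would still need settling.

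It is also fair to say that four days is the SAP's accepted minimum at every visit, and that a recent baseline has a purpose when subjects may be re-screened once. Both are true. Neither explains dropping days from the same diary week.

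A reader might infer that most baselines rest on four days, or that the trial in effect loses dozens of subjects. The SAP does not support this: the scheduled diary loses at most one day, and the larger figures require every subject to have a four-day baseline. A reader might also infer bias from setting a shortened baseline against a full later week. The choice of days depends on timing around randomization and acts alike in both arms, and the model adjusts for baseline and baseline by visit. Nor does the SAP give grounds to expect a weekday effect.

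**Conclusion.** The point holds as a minor specification flaw. As written, the baseline rule scores a complete diary from the seven days before randomization on 6 days, and one ending three or more days earlier on 4. Those counts follow from the SAP's text alone. The cost is precision only, with no bias and no type I error inflation. At the assumed correlation of 0.7 it is about 0.5-1.2% of the adjusted variance for 6-day baselines and about 2-5% at the extreme where all baselines have 4 days. These percentages rest on assumed standard deviations, correlation and daily-error structure, and the true figure depends on a distribution of gaps that the SAP does not report. The case for changing the rule is that the loss is avoidable, not that it is large.

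**What to change.** Replace the baseline sentence in Appendix C.2 with a rule in line with the post-baseline order: among 7-day periods that end on or before the randomization date (inclusive) and lie within the last screening attempt, use the one with the fewest missing daily scores, with at least 4 available; among ties, use the one closest to randomization. A complete diary then contributes all seven days at any gap, and the limit to the last screening attempt prevents an older, fuller diary from displacing the current one.

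Anchoring the window on the last day with a valid entry would be less safe. With a full diary on Days -11 to -5 and one stray entry on Day -1, the window Days -7 to -1 holds exactly four scores (Days -7, -6, -5 and -1), so the week is cut short again. The rule above recovers all seven.

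The cost is one sentence and a small programming change, with no new data and no subjects lost. The only downside is that the chosen week may end a few days earlier than under the present rule.
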